6.3 Hepatotoxicity Stopping and Rechallenge Rules

Subjects with abnormal hepatic laboratory values (ie, alkaline phosphatase [ALP], aspartate aminotransferase [AST], alanine aminotransaminase [ALT], total bilirubin [TBL]) and/or international normalized ratio [INR] and/or signs/symptoms of hepatitis (as described below) may meet the criteria for withholding or permanent discontinuation of Amgen investigational product or other protocol-required therapies as specified in the Guidance for Industry Drug-Induced Liver Injury: Premarketing Clinical Evaluation, July 2009.

6.3.1 Criteria for Permanent Discontinuation of Amgen Investigational Product and Other Protocol-required Therapies Due to Potential Hepatotoxicity

Amgen investigational product and other protocol required therapies should be discontinued permanently and the subject should be followed according to the recommendations in [Appendix A](#) (Additional Safety Assessment Information) for possible drug-induced liver injury (DILI), if ALL of the criteria below are met:

- TBL > 2x upper limit of normal (ULN) or INR > 1.5
- AND increased AST or ALT from the relevant baseline value as specified below:

Baseline AST or ALT value	AST or ALT elevation
< ULN	> 3x ULN

- AND no other cause for the combination of the above laboratory abnormalities is immediately apparent; important alternative causes for elevated AST/ALT and/or TBL values include, but are not limited to:
 - Hepatobiliary tract disease
 - Viral hepatitis (eg, Hepatitis A/B/C/D/E, Epstein-Barr Virus, cytomegalovirus, Herpes Simplex Virus, Varicella, toxoplasmosis, and Parvovirus)
 - Right sided heart failure, hypotension or any cause of hypoxia to the liver causing ischemia.
 - Exposure to hepatotoxic agents/drugs or hepatotoxins, including herbal and dietary supplements, plants and mushrooms
 - Heritable disorders causing impaired glucuronidation (eg, Gilbert's Syndrome, Crigler-Najjar syndrome) and drugs that inhibit bilirubin glucuronidation (eg, indinavir, atazanavir)
 - Alpha-one antitrypsin deficiency
 - Alcoholic hepatitis
 - Autoimmune hepatitis
 - Wilson's disease and hemochromatosis
 - Nonalcoholic Fatty Liver Disease including Steatohepatitis (NASH)
 - Non-hepatic causes (eg, rhabdomyolysis, hemolysis)

6.3.2 Criteria for Conditional Withholding of Amgen Investigational Product and Other Protocol-required Therapies Due to Potential Hepatotoxicity

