14. APPENDICES

Appendix A. Additional Safety Assessment Information

Adverse Event Grading Scale

Refer to the NCI Common Terminology Criteria for AEs (CTCAE) Version 4.0 for AE grading and information. The CTCAE is available at the following link:

http://ctep.cancer.gov/protocolDevelopment/electronic_applications/ctc.htm.

Drug-induced Liver Injury Reporting & Additional Assessments Reporting

To facilitate appropriate monitoring for signals of DILI, cases of concurrent AST or ALT and TBL and/or INR elevation according to the criteria specified in [Section 6.3](#) require the following:

- The event is to be reported to Amgen as a serious adverse event within 24 hours of discovery or notification of the event (ie, before additional etiologic investigations have been concluded)
- The appropriate eCRF (eg, Event eCRF) that captures information necessary to facilitate the evaluation of treatment-emergent liver abnormalities is to be completed and sent to the Amgen.
- Other events of hepatotoxicity and potential DILI are to be reported as serious adverse events if they meet the criteria for a serious adverse event defined in [Section 9.2.2](#).

Additional Clinical Assessments and Observation

All subjects in whom investigational product(s) or protocol-required therapies is/are withheld (either permanently or conditionally) due to potential DILI as specified in [Section 6.3.1](#) and [Section 6.3.2](#) or who experience AST or ALT elevations >3 x ULN are to undergo a period of “close observation” until abnormalities return to normal or to the subject’s baseline levels. Assessments that are to be performed during this period include:

- Repeat AST, ALT, ALP, bilirubin (total and direct), and INR within 24 hours
- In cases of TBL > 2x ULN or INR > 1.5, retesting of liver tests, BIL (total and direct), and INR is to be performed every 24 hours until laboratory abnormalities improve
- Testing frequency of the above laboratory tests may decrease if the abnormalities stabilize or the investigational product(s) or protocol-required therapies has/have been discontinued AND the subject is asymptomatic
- Initiate investigation of alternative causes for elevated AST or ALT and/or elevated TBL:
- Obtain complete blood count (CBC) with differential to assess for eosinophilia

- Obtain serum total immunoglobulin IgG, Anti-nuclear antibody (ANA), Anti Smooth Muscle Antibody, and Liver Kidney Microsomal antibody 1 (LKM1) to assess for autoimmune hepatitis

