10.6.2 Laboratory Test Results

Descriptive statistics will be provided for actual values and changes from baseline in select laboratory parameters at each protocol-specified scheduled visit. Laboratory analytes are provided in the protocol [section 7.2](#). Lab shift tables using the CTCAE v4.03 or later grading will be used for the select analytes of interest, when applicable.

In addition, CK and liver function test (LFT) abnormalities will be assessed by the incidence overall and by visits of the following categories:

- CK > 5 x ULN
- CK > 10 x ULN
- ALT or AST > 3 x ULN
- ALT or AST > 5 x ULN
- Total bilirubin > 2 x ULN
- (ALT or AST > 3 x ULN) and Total bilirubin >2 x ULN and Alkaline Phosphatase < 2 x ULN

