Appendix B. Analytical Study Week Assignments

Selected endpoints will be summarized by scheduled study visits in descriptive analyses.

Since the actual visits may not exactly coincide with their scheduled visit day, the actual visit day is mapped to the study visit generally by non-overlapping consecutive intervals covering the entire time continuum. The mapping intervals for all distinct schedules are summarized in the following tables.

Scheduled Visit Week	Week 2	Week 8	Week 10	Week 12	Week 24	Week 36	Week 48	Week 52	Week 54 EOS Phone Call
Scheduled Visit Day	15	57	71	85	169	253	337	365	379
Vital Signs		(1, 63]	(63, 77]	(77, min(91, first dose date of OLE)]	(min(91, first dose date of OLE), 210]	(210,294]	(294,350]	>350	
Fasting Lipids	(1, 35]	(35, 63]	(63, 77]	(77, min(91, first dose date of OLE)]	(min(91, first dose date of OLE), 210]	(210,294]	(294,350]	(350,378]	
Lp(a), ApoA1, ApoB			(1, 77]	(77, min(91, first dose date of OLE)]	(min(91, first dose date of OLE), 210]	(210,294]	(294,350]	(350,378]	
PK, PCSK9	(1, 42]		(42, 77]	(77, min(91, first dose date of OLE)]				(min(91, first dose date of OLE), 378]	
Hematology and Chemistry		(1, 70]		(70, min(91, first dose date of OLE)]				> min(91, first dose date of OLE)	
Physical Exam, hsCRP, Urinalysis, HbA1c, Biomarkers, anti-evolocumab antibodies				(1, min(91, first dose date of OLE)]				> min(91, first dose date of OLE)	
Weight, waist circumference								> 1	

Handling multiple records assigned to an analytical study week:

If there is more than one record in a study week interval, the analytical record for that specific study week will be defined as the record closest to the scheduled visit day of that specific study week ($7 \times$ study week + 1). If two records are equidistant from the scheduled day, then the earlier record will be chosen. If there are multiple records on the same day, the last record will be used.

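### By-visit CK and liver threshold counts keep one record per wide window, so an exceedance can be left out; SAP 10.6.2 should name a worst-value record set

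*SAP*

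**What the plan says.** SAP Section 10.6.2 states: "CK and liver function test (LFT) abnormalities will be assessed by the incidence overall and by visits of the following categories". The categories are CK above 5 and 10 times ULN, ALT or AST above 3 and 5 times ULN, total bilirubin above 2 times ULN, and one combined liver category. The section also mentions CTCAE grade shift tables.

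SAP Section 6.3 sends parameter measurements to study weeks through Appendix B, which describes its scope as "Selected endpoints will be summarized by scheduled study visits in descriptive analyses". For hematology and chemistry, Appendix B has three post-baseline windows:

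- Week 8: after day 1, up to day 70.
- Week 12: after day 70, up to the earlier of day 91 and the first open-label dose.
- Week 52: everything later.

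When a window holds several records, "the analytical record for that specific study week will be defined as the record closest to the scheduled visit day" is kept. For ties, "If two records are equidistant from the scheduled day, then the earlier record will be chosen". For repeats, "If there are multiple records on the same day, the last record will be used".

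Protocol Table 1 schedules chemistry at screening, Day 1 and Weeks 8, 12 and 52. Protocol Appendix A adds follow-up after an AST or ALT above 3 times ULN, or when product is withheld for possible liver injury: "Repeat AST, ALT, ALP, bilirubin (total and direct), and INR within 24 hours". Protocol 10.5.5 plans shifts from baseline to the highest post-baseline grade. SAP 10.1 says the blinded-period analyses will not be repeated at the final analysis, while the extension summaries will be updated.

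**The concern.** Choosing the record nearest the target day is sensible for a mean at a visit. It suits a threshold count poorly, because the question there is whether a subject crossed the limit at any time in the interval. Unscheduled and repeat samples are often taken because something looks wrong, and for liver tests the protocol requires repeats. A rule based only on timing can then replace the abnormal value with the follow-up value.

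Subjects enter this trial because of muscle-related statin intolerance, so CK is a main tolerability measure, and with about 60 subjects a single exceedance matters to the reader. An asymptomatic rise may appear only in the laboratory tables, because Protocol 9.2.1 says abnormal results without clinical significance are generally not recorded as adverse events.

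**Working it through.** The plan states no figure to reproduce here, so the check applies the Appendix B rules as written.

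**Inputs.** The windows and selection rules are from SAP Appendix B. The target day is 7 × week + 1: day 57 (Week 8), day 85 (Week 12) and day 365 (Week 52). The visit tolerance of ±3 days is from Protocol 7.2.3. Two assumptions are made for illustration: the first open-label dose is on day 85, and a spike is CK at 12 times ULN with all other values normal.

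**Window widths.** Week 8 covers days 2 to 70 (69 days). Week 12 covers 15 days if it closes on day 85 (85 − 70) and at most 21 (91 − 70). The Week 52 slot runs from day 86; up to day 365 that is 365 − 85 = 280 days, and it stays open afterwards. At most three post-baseline chemistry records per subject can enter a by-visit table.

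**Six histories.** The retained record has the smallest |day − target|.

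| Case | Spike | Other record in the window | Distances, spike vs other | By-visit CK > 10 × ULN |
|---|---|---|---|---|
| A | day 30, unscheduled | day 57 | 27 vs 0 | dropped |
| B | day 57 | repeat day 58 | 0 vs 1 | kept |
| B2 | day 55, in-window visit | repeat day 57 | 2 vs 0 | dropped |
| C | day 200, extension | day 365 | 165 vs 0 | dropped |
| D | day 200, extension | none yet | only record | kept, labelled Week 52 |
| E | day 57 | same-day retest | same day, last used | dropped |

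The rule drops four of six. A flag based on any post-baseline record counts all six.

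**Required liver repeats.** Suppose an abnormal Week 8 value falls on day d, before day 57, and the repeat comes r days later. The repeat lands nearer the target when r < 2 × (57 − d):

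- d = 54: r < 6, so a repeat 1 to 5 days later displaces the abnormal value.
- d = 55: r < 4, so 1 to 3 days.
- d = 56: r < 2, so 1 day.

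A next-day repeat therefore always displaces an abnormal Week 8 value from days 54 to 56, all of which lie inside the visit tolerance. The same arithmetic applies at Week 52 for days 362 to 364. An abnormal value on day 57 or later is kept against any later-day repeat.

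**Other tables.** SAP 10.6.2 asks for an overall incidence as well, but does not say whether it draws on all records or on the Appendix B analytical records. The same silence applies to the shift tables: Protocol 10.5.5 specifies the maximum grade, but neither document says over which records the maximum is taken.

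**The case against.** The strongest reply is that the by-visit table is only one of several. An overall incidence is not a by-visit summary, Appendix B limits itself to summaries by scheduled visit, and an ordinary reading of overall incidence counts any post-baseline exceedance. The maximum-grade shift in Protocol 10.5.5 still stands, since SAP Section 11 drops only the physical measurements. This is right. A reader might infer that the overall counts and shift tables are also under-counted, or that the report could show zero despite an event; the documents do not support that. What remains is that the record set for these tables is unstated.

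A reader might also infer that spikes always vanish, or that only the Week 52 sample can appear in the extension. Neither follows. A spike survives when it is the closest or only record (cases B and D). The extension slot takes whichever later record is nearest day 365, so an earlier sample appears when no Week 52 sample exists, for instance at the primary-analysis cut-off. When open-label dosing starts at the Week 12 visit, that window closes the same day, so a next-day repeat cannot displace the Week 12 value. The single extension slot also mirrors the schedule, which has no chemistry at Weeks 24, 36 or 48.

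The required repeats are triggered by liver findings, not by CK alone, and nothing shows that same-day retests would be usual. Serious cases have another route: Protocol Appendix A makes concurrent transaminase and bilirubin or INR elevation under Section 6.3 a serious adverse event. That route does not cover an asymptomatic CK or transaminase rise judged not clinically significant.

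Finally, a reader might expect the combined liver category to mirror Protocol 6.3.1, which has no ALP condition and accepts INR. The documents do not require this: 6.3.1 is a stopping rule, and INR is not in the scheduled analyte listing.

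**Conclusion.** The point holds for the by-visit threshold counts. Followed as written, Appendix B omits an exceedance whenever another record in the same window lies nearer the target day, or is the last of several on one day. For the overall incidence and the grade shifts, the finding is an unstated record set, not a demonstrated under-count.

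The size cannot be given as a rate, because the documents contain no frequency of exceedances or of unscheduled samples. The four-of-six result shows how the rule behaves in chosen cases and does not estimate how often it matters. The window widths assume open-label dosing starts on day 85. Efficacy is unaffected, and SAP Table 2 plans no inference on safety laboratory data. This is an inexpensive improvement to safety reporting, most useful in the extension, where one record stands for at least 280 days in a subject followed to day 365.

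**What to change.** In SAP 10.6.2, with a cross-reference in Appendix B, state that the CK, ALT/AST and bilirubin threshold counts (overall by period, and by visit interval) and the CTCAE grade shifts use the worst value among all scheduled, unscheduled and repeat post-baseline records in the period or interval. Keep the closest-record rule for by-visit means and other descriptive statistics.

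Because SAP 10.1 rules out repeating the blinded-period analyses, apply the rule to the final extension analysis. For the completed blinded-period tables, state in the study report which records fed the overall counts, the by-visit counts and the shifts.

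The cost is a few sentences and minor programming. Counts may become slightly less favourable, and by-visit threshold tables will rest on different records from the by-visit means, which a footnote should say.

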Appendix C. Common Terminology Criteria for AEs (CTCAE)

Refer to the NCI Common Terminology Criteria for AEs (CTCAE) for AEs and lab shift grading and information. The CTCAE is available at the following link:

<http://evs.nci.nih.gov/ftp1/CTCAE/About.html>
